**Table 3. Study outcomes and anticipated results at the end of 4-week dietary intervention**

Primary outcome variable	Method of detection	Baseline to Visit 3 change
Body weight	Weight scale	↓
Waist circumference	Tape measure	↓
Body fat percentage	DEXA	↓
Blood pressure	Blood pressure cuff	↓
Energy expenditure	Indirect calorimetry	↓
Lipid level	Enzymatic assay	↓
Glucose and insulin level	Enzymatic assay and ELISA	↓
Fructose level	Enzymatic assay	↓
Uric acid level	ELISA	↓
Creatinine level	ELISA	↓
Urinary ketone level	Enzymatic assay	↓
Carotid-femoral PWV	SphygmoCor XCEL device	??

Abbreviations: DEXA, dual-energy X-ray absorptiometry; Indir. cal., indirect calorimetry; ELISA, enzyme-linked immunosorbent assay; PWV, pulse wave velocity

### Schedule of Events

#### *Screening*

Twenty overweight/obese subjects (10 men and 10 women, 30-55 yrs old) will each participate in the 4-week dietary intervention and 4-week follow-up phase. Eligibility is determined through interactions between study staff and the subjects (initial phone conversation and a screening visit). During the screening visit at the clinical research center (CRC), after signing the consent form, the subject undergoes a fasting blood draw (40 ml) to rule out the presence of diabetes and blood is drawn for serum HbA1c, complete blood count, thyroid, liver (liver enzymes and hepatitis), and kidney function, and a lipid panel are measured. Medical information is obtained including DOB, gender, ethnic/racial category, height, body weight (history of body weight) and medical history (medication use, smoking history). The subject is fed breakfast after blood draw and fills out surveys to assess physical activity, typical food intake, food cravings and sleep quality.

#### *Baseline visit 1*

When results from the screening visit are available, eligible/interested subjects are scheduled for their baseline visit 1 after which, they would start the 2-week feeding regimen. The subject is instructed to

[figure not shown]
## PROTOCOL: Project

Project Title: "A short term evaluation of a structured weight loss plan in overweight and obese adults"  
 Version 1 Date: March 18, 2016

wear a study-provided Fitbit Flex® device (Fitbit, San Francisco, CA) four days before the baseline test and during the 4-week dietary intervention to assess the physical activity level. The baseline visit will take place in the CRC. Before the participant comes to the CRC on the study day, he/she is instructed to collect a fasting urine sample. Upon arrival, the participant first voids and then the study staff take the vital signs and measure the height and weight. A catheter is inserted into the vein of one arm to collect 60 ml whole blood. Next, DEXA scan is performed to assess body composition. The resting energy expenditure is subsequently determined using an indirect calorimetry (metabolic cart). The subject lies comfortably in a bed on his/her back and the metabolic cart collects and analyzes the breath to calculate the total energy expenditure. This procedure will take about 30 minutes before continuing for the aortic PWV testing. The subject lies supine again for the aortic PWV testing (**figure 3**).

Carotid-femoral PWV measurement is considered the gold standard, non-invasive index of arterial stiffness. The SphygmoCor XCEL device is used for this assessment, which allows for the simultaneous acquisition of carotid (via tonometer) and femoral (via cuff) pulse waves following the established guidelines (13, 14). Transit time between carotid and femoral pressure waves is calculated using the foot-to-foot method (**figure 3**). Wave 'foots' are identified using intersecting tangent algorithms. PWV is calculated as distance traveled by the pulse wave (i.e., femoral location-sternal notch minus sternal notch-carotid location) divided by pulse transit time. The intra-subject reproducibility for the measurement (2 wks apart, n=15), is as follows: measurement #1, 6.13 m/s; measurement #2, 6.19 m/s, resulting in an average % difference of the two measurements of 0.98% with a SD of that difference among the subjects of 8%. All measurements of PWV are performed by the same investigator.

Figure 3. Aortic Pulse Wave Velocity (PWV)

*Consumption of two-week specially formulated diet*

The study is designed to first measure how well the commercial meals of low carbohydrate and reduced calorie result in the weight loss over two weeks and then assess the effect of subsequent consumption of a self-prepared, energy-restricted, low-carbohydrate meals on body weight and CV function. All foods given to the subject are commercially available and sold in supermarkets. The subject is assigned randomly to one of two dietary patterns in which all the food is provided for two weeks. Diet 1: The "Grab-and-Go" plan provides Atkins shakes and bars for breakfast, lunch, and snacks. For dinner the subject is given a freshly-prepared meal. Diet 2: The "Jump-Start" plan provides Atkins frozen meals at breakfast, lunch and dinner and these meals are supplemented with fresh salads and vegetables. The reason for the two diets is to understand how subjects like the diets. The diets have the same calories, are otherwise similar in content, and not expected to differ in their ability to cause weight loss.

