**Summary of Study Objectives**

We will accomplish the following specific aims:

**Aim 1 (weight loss):** To induce weight loss, overweight/obese subjects will be fed with a 2-week calorie-restricted diet. This specially formulated diet (see Appendix) will be low in carbohydrates. After this two weeks, the subjects will prepare their own food based on the Atkins online diet program for subsequent 2 weeks. ***Hypothesis 1:*** *After four weeks of a calorie-restricted diet feeding, the subjects will lose 3-6% of their body weight.*

**Aim 2 (arterial stiffness improvement):** To quantify arterial stiffness improvement by measuring aortic pulse-wave velocity (PWV). ***Hypothesis 2:*** *After four weeks of feeding, the subjects will have lower serum uric acid level and lower aortic PWV. Further, the female participants will have even more improvement of PWV compared to men.*

**AIM 3 (lifestyle impact on body weight):** To assess the impact of individual lifestyle factor on the change of body weight, blood pressure and heart rate. ***Hypothesis 2:*** *During the four weeks of follow-up, the changes of subjects' body weight, blood pressure and heart rate will reflect their lifestyle.*

**Impact:** The present study to evaluate the effect of a calorically-restricted diet on body weight and arterial stiffness in overweight and obese adults. The data generated by this study will determine whether arterial stiffness can be improved by short-term low carbohydrate diet, and the potential mechanism by which uric acid level impacts CV risk in overweight and obese adults, especially in women. This study will also provide the important preliminary data for an NIH R01 grant submission.

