**Study design and data analysis**

Our statistical analysis plan, designed in consult with [name], is based both on our preliminary data (**fig. 2**) and data from the increased body of literature that has been generated over the past few years (9-12). The present study is designed to generate data from a future grant and thus, we will use the data generated here for future sample size estimation. For analysis, study group characteristics will be summarized with descriptive statistics and the data will be analyzed as % and absolute change.

Paired t-tests will be used to test if the within-group changes are significantly different from zero, and a one-way analysis of variance applied to the "change scores" will be used to test for group (sex)

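### Allocation to the two diets is not said to be stratified by sex, and the analysis by sex has no diet term: a cheap, low-priority improvement

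*Combined protocol and SAP*

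**What the plan says.** Under the heading on consumption of the two-week specially formulated diet, the protocol states: "The subject is assigned randomly to one of two dietary patterns in which all the food is provided for two weeks". No section gives the method, ratio, block size or any stratification factor. The stated purpose is acceptability: "The reason for the two diets is to understand how subjects like the diets". On comparability it adds: "The diets have the same calories, are otherwise similar in content, and not expected to differ in their ability to cause weight loss".

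The Screening section fixes the sample: "Twenty overweight/obese subjects (10 men and 10 women, 30-55 yrs old) will each participate" in the intervention and follow-up. The second hypothesis, in the Summary of Study Objectives, is that "the female participants will have even more improvement of PWV compared to men". In the section on study design and data analysis, "a one-way analysis of variance applied to the 'change scores' will be used to test for group (sex" differences in change. Diet does not appear in that model.

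**The concern.** The investigators introduce a second factor, diet, alongside the one they want to compare, sex. Neither the allocation as described nor the analysis as described keeps the two apart. With 10 subjects per sex, chance can put noticeably more women than men on one plan. Any difference between the plans in their effect on an outcome then appears partly as a sex difference.

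The plans differ in form: shakes and bars with one fresh dinner, against three frozen meals with salads and vegetables. The expectation of no difference is stated for weight loss only. It is not stated for uric acid, blood pressure or PWV, and PWV carries the sex hypothesis.

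The liking question is affected too. Interim visit 2 collects craving, appetite and satisfaction straight after the feeding period. If one plan is taken mostly by women, a difference in liking cannot be separated from a difference in food preference between the sexes.

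**Working it through.** The plan gives no figure on this point to reproduce. The inputs from the protocol are 10 men, 10 women and two diets. The 1:1 ratio, the two-sided 5% level and the diet effects (0.2, 0.5 and 0.8 SD of the change score) are assumptions.

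1. **Simple 1:1 randomisation.** The numbers of men and women on a given diet are independent Binomial(10, 0.5). Their difference has the distribution of X − 10 with X ~ Binomial(20, 0.5).
   - Difference of 4 or more: 2 × (1 + 20 + 190 + 1,140 + 4,845 + 15,504 + 38,760) / 2^20 = 120,920 / 1,048,576 = 11.5%.
   - By the same method: 2 or more, 50.3%; 3 or more, 26.3%; 6 or more, 1.2%.

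2. **Total forced to 10:10, not stratified.** P(k men on a given diet) = C(10,k)² / C(20,10), with C(20,10) = 184,756.
   - Split of 7 against 3 or worse: 2 × (1 + 100 + 2,025 + 14,400) / 184,756 = 17.9%.
   - 6 against 4 or worse, 65.6%; 8 against 2 or worse, 2.3%.

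3. **Leakage into the sex contrast** = (difference in counts / 10) × diet effect. At 7 against 3 the factor is 0.7 − 0.3 = 0.4, which gives 0.08, 0.20 and 0.32 SD for diet effects of 0.2, 0.5 and 0.8 SD.

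4. **Noise for comparison.** The standard error of the sex difference is SD × √(2/10) = 0.45 SD. The 0.20 SD shift is 0.20 / 0.45 = 0.44 of a standard error.

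5. **Illustration for PWV.** The Baseline visit 1 section gives 8% as the SD of the two-week repeat difference. If the change score had that SD, a 0.5 SD diet effect would be 4 percentage points. The leak at 7 against 3 would be 0.4 × 4 = 1.6 points, against a standard error of 8 × √0.2 = 3.6 points.

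6. **Type I error of the unadjusted sex test** (200,000 simulated trials per setting). Over all unstratified allocations it stays at 4.9–5.1% for every diet effect tried. Given a difference in counts of 3 or more:

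| Assumed diet effect | Type I error |
|---|---|
| 0 | about 5% |
| 0.2 SD | 5.3–5.4% |
| 0.5 SD | 6.1–6.8% |
| 0.8 SD | 7.8–9.0% |

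7. **Balancing or adjusting.** With 5:5 in each sex, an additive diet effect contributes nothing to the sex contrast. If diet is then left out of the model, its effect stays in the residual and the test becomes conservative: 4.3% at 0.5 SD and 3.5% at 0.8 SD. Adjusting without balancing costs precision: at 7 against 3 the correlation of diet with sex is 0.4, so the variance of the sex contrast rises by the factor 1 / (1 − 0.4²) = 1.19. At 5:5 the factor is 1.

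**The case against.** The strongest reply is that there may be almost no diet effect to leak. The protocol says the diets match in calories and resemble each other in content. The meal composition is in an appendix that is not in the text available here, so no material difference can be shown. The plans also differ for two weeks only. Everyone then follows the same online programme with food prepared at home, and the main comparison is from baseline to visit 3, at four weeks. No PWV measurement is listed at interim visit 2, so a diet effect on PWV would have to outlast two weeks on a common regimen. This stands and is the main reason the point is minor. It does not close the point, because similar content is not a statement of equal effect on PWV, uric acid or blood pressure.

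It is also fair to say that this is a pilot, that sex is not randomised in any case, and that no test between diets is planned. In the investigators' earlier study, men and women already differed in baseline added sugar (9.3% against 16.6% of energy). Chance imbalance in diet is small beside that. But it is the part that the design can remove at almost no cost, and the data are meant to inform future sample-size estimation.

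Three stronger readings are tempting and are not supported.
- A reader might infer that the protocol specifies unstratified randomisation. It is silent, and the percentages above hold only if stratification is indeed absent.
- A reader might infer a systematically biased sex test. Averaged over allocations, its type I error stays near 5%; the distortion is conditional on the one allocation drawn.
- A reader might take the chance that at least one sex splits 7:3 or worse, 1 − (1 − 0.344)² = 57%, as the risk of confounding. It is not: if both sexes lean the same way to the same extent, diet and sex are uncorrelated and nothing leaks.

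**Conclusion.** The point holds in a limited form. The randomisation method and any stratification by sex are unspecified, and the sex comparison carries no diet term. If allocation is unstratified, a split as uneven as 7 against 3 has a chance of roughly one in eight or nine (simple) to one in six (10:10 total). The resulting shift in the sex contrast is then under half a standard error for a diet effect of 0.5 SD. That effect size is an assumption; with no diet effect the shift is zero. For the liking comparison a diet difference is itself the question, so mixing with sex matters there even if the diets act identically on the vascular and metabolic outcomes. This is a low-priority improvement and does not threaten the study's validity.

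**What to change.** State the randomisation method. Randomise to diet separately within men and within women, in permuted blocks whose sizes add up to 10, so that 5 men and 5 women receive each plan. Replace the one-way ANOVA of change scores by a two-factor model, sex + diet. Keep the diet term even when allocation is balanced, since leaving it out makes the sex test conservative if the diets do differ. Report liking by diet within sex as well as overall.

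The cost is two allocation lists instead of one, and one of the 18 residual degrees of freedom (leaving 17). No subjects, visits or measurements are added. If allocation has already been made without stratification, the diet term alone can still be added, at the price of the variance increase shown above (19% at 7 against 3).

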**PROTOCOL: Project**

Project Title: "A short term evaluation of a structured weight loss plan in overweight and obese adults"

Version 1 Date: March 18, 2016

**Beverages:** The subject will be asked to consume 8, 8-oz glasses of liquids per day. The subject may also consume coffee or tea without nondairy creamer added, but non-caloric sweeteners, and/or 2 oz of cream per day to the coffee or tea are allowed. Diet soda or other non-caloric beverages are allowed.

We anticipate no medical risks from consuming these diets for 2 weeks. The subjects will be asked to consume only the prescribed foods given to them and no other foods. This may get boring or the subject may experience frustration due to limited food and beverage choices.

***Interim visit 2***

Before the subject comes for this visit, he/she will be instructed to collect a urine sample at home as he/she did on the Baseline visit 1 and bring the urine sample to the CRC. The study staff will assess the body weight, waist circumference, heart rate and blood pressure. After these measurements, the subject fills out a questionnaire to assess the food craving, appetite and satisfaction on the meal plan. Blood will be collected during this visit (30 ml). Upon completion of the two-week feeding period, the subjects are instructed on how to use the Atkins online diet program (<https://www.atkins.com/how-it-works/free-tools>) to prepare their own meals which should continue to be restricted in energy and reduced in carbohydrate at home for another two weeks.

***Follow-up visit 3***

Upon finishing the 4-week dietary intervention, the subject reports for visit 3. All the procedures performed will be the same as the ones performed during the baseline test (collection of 60 ml whole blood) and only questionnaires on food craving, appetite and diet consumption will be filled out.

***Follow-up visit 4 and final visit 5***

After the follow-up visit 4, the subject returns to the CRC two and four weeks later to assess the original four-week dietary intervention's impact on the longer-term blood pressure and heart rate. Before coming to the visit 4 and 5, the subject is instructed to collect a urine sample first thing in the morning and come to the CRC fasted. We will measure the body weight, blood pressure, heart rate and collect 30 ml whole blood at visit 4 and 60 ml blood at visit 5 to assess plasma glucose, insulin, TG, fructose and uric acid levels. Questionnaires will be administered to assess food intake pattern and food cravings at visit 5.

**Human Subjects Involvement and Characteristics*****Recruitment and informed consent***

The study population includes male and female subjects with BMI (27-40 kg/m^2) and age 30-55y (pre-menopausal women only). The recruitment process will include the typical flyers and notices put in public spaces. These recruitment materials will be posted around the University of Missouri campus, as well as other public places such as swimming pools, churches, and grocery stores. The flyers will state the purpose of the study, eligibility criteria and will tell subjects to call into our clinical trial office for more information. On these calls, the study will be described briefly. A checklist will be gone through to perform initial screening for age, gender, and health status. Subjects who are eligible by the phone conversation will be scheduled for a screening visit and they will be given the consent form (by post,

## PROTOCOL: Project

Project Title: "A short term evaluation of a structured weight loss plan in overweight and obese adults"

Version 1 Date: March 18, 2016

email or fax) before they come to the screening visit. They may also bring a friend or family member to the visit. The consent form states the purpose of the study, risks, inconveniences, discomforts, and other important information about the study and has been prepared in lay terms so that it is easy to understand. During the screening visit the form is reviewed comprehensively. The subject is instructed to ask questions about any words or information that they do not clearly understand and questions will be answered by the PI and her staff. This will enable us to determine the subject's comprehension of the study. The consent form will be signed before any study procedures are initiated.

**Criteria for inclusion**

1. Men and premenopausal women
2. 30-55 years of age
3. Sedentary lifestyle, defined as less than three sessions of activity per week, or sessions less than 20 minutes per occasion, or less than 5000 steps per day
4. Must be able to speak, read, and write English (due to the small sample size and pilot nature of this study)
5. Overweight/obese subjects with BMI 27.0 - 40.0 kg/m^2 and any one of the following characteristics of the metabolic syndrome:
  - A. Serum HDL cholesterol <40 mg/dL (1 mmol/L) in men and <50 mg/dL (1.3 mmol/L) in women
  - B. Blood pressure ≥130/85 mmHg
  - C. Fasting plasma glucose ≥100 mg/dL (5.6 mmol/L)
  - D. Waist circumference in men of >102 cm (40 in) and in women of >88 cm (35 in)
  - E. Serum triglycerides (TG) ≥150 mg/dL (1.7 mmol/L).

**Criteria for Exclusion**

1. Abnormal thyroid function or known liver disease
2. Diabetes or fasting glucose ≥ 125 mg/dL
3. Use of medications that interfere with protein, carbohydrate or lipid metabolism (e.g., fish oil capsules)
4. Occasional or regular tobacco use
5. History of gout
6. Uncontrolled hypertension
7. Pregnant or peri-menopausal
8. Vegetarian food restrictions (the diets consumed contain some meat, eggs and dairy)
9. Alcohol intake: females > 70 g/wk, males >140 g/wk
10. Moderate or vigorous-intensity physical activity, defined as more than 150 minutes per week of moderate-intensity, or 75 minutes a week of vigorous-intensity aerobic physical activity, or an equivalent combination of both.

**Potential risks**

Physical risks may include:

1. Blood drawing: During the screening, baseline and follow-up visits, blood will be drawn. The risk of blood drawing may include temporary discomfort from the needle stick, bruising, and rarely, infection. A black and blue mark may result from placement of a catheter; this can be painful, but it carries no significant risks. The total blood loss for the entire study is 300 ml.

**PROTOCOL: Project**

Project Title: "A short term evaluation of a structured weight loss plan in overweight and obese adults"  
Version 1 Date: March 18, 2016

**2. Indirect calorimetry:** The baseline and follow-up tests include calorimetry tests which are painless. However, persons who are uncomfortable in confined spaces may find this test slightly stressful.

**3. DEXA:** The radiation during DEXA is equivalent to about 2% of the average radiation dose from all sources (natural background radiation, consumer appliances, radon gas, medical tests, etc.) that a person in the United States received each year.

**4. Psychological stress:** The psychological stress from participation in this study is minimal. However, some of the questions about food intake and physical activity may make the subjects feel uncomfortable.

**5. Arterial stiffness and blood pressure:** When assessing carotid-femoral PWV, the blood pressure cuff will squeeze the arm and leg tightly; however, any discomfort will be alleviated as soon as the pressure in the cuff is released.

**6. Loss of confidentiality:** Any time information is collected; there is a potential risk for loss of confidentiality. Every effort will be made to keep subject's information confidential; however, this cannot be guaranteed. The information collected includes: age, ethnicity, gender, height, body weight, blood pressure, and blood test results (e.g., glucose, blood fats) and hormones (insulin). Finally, the investigator will report information to authorities in order to prevent serious harm to the subject or to others. If the Investigators suspect child, elder or disabled person abuse, they will report such concerns to proper authorities as required by law.

**7. Risks to Embryo, fetus or breast-fed infant and sperm:** The effects of the DEXA on the female or male reproductive systems or on a developing fetus are unknown but could cause harm. For this reason, the subject is required to avoid getting pregnant during this study. Pregnancy status will be checked using a blood test before the DEXA.

**8. Other risks:** There may possibly be other side effects that are unknown at this time.

